7.7 CORE LABORATORIES: ECHOCARDIOGRAPHY, AND EKG MONITORING

Electrocardiographic monitoring will be performed by continuous 3-4 week monitors as described. We have secured a commitment from a qualified vendor to provide with storage of *continuous data* (i.e. all the heart beats) for the 3-4 week monitoring time that will allow precise determination of the AF burden (percentage of time in AF). *Data will be reviewed by technicians unaware of the treatment mode, thus AF occurrence and AF burden quantification will be blinded.* Additionally, analysis such as heart rate variability may be performed: If VOM ethanol causes effective vagal denervation, and vagal innervation modulates dynamics of heart rate variability¹²³ then we expect differences between the two treatment groups. The core echocardiographic laboratory is a national leader in echocardiography with particular expertise in LA function.^{114b} LA volumes, ejection fraction and strain will be collected as described and reviewed and analyzed in the echocardiography core laboratory at Houston Methodist Hospital.^{114ab}

Alternate rhythm monitoring

Certain patients may be eligible for implantation of a miniaturized subcutaneous recording device (Medtronic LinQ device) or other equivalent implanted permanent monitoring devices. These implanted devices provide continuous electrocardiographic monitoring for up to 3 years including data on atrial fibrillation or flutter burden, episode duration per day and other quantified data. For patients that choose to have this kind of monitoring, AF data will be quantified for the primary and secondary endpoints using this device as opposed to 3-4 week electrocardiographic monitoring.

Certain patients may already have an implanted pacemaker previously inserted prior to study enrollment. These devices yield interrogation reports that provide sufficient data on atrial fibrillation or flutter burden, episode duration per day and other quantified data. For patients that already undergo this kind of monitoring, AF data will be quantified for the primary and secondary endpoints using these devices as opposed to 3-4 week electrocardiographic monitoring.

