- 2. Thirty-day (30D) follow-up (+/- 10 days).** Follow up evaluation will include an EKG, assessment for complications including a targeted physical exam and a review of adverse events and concomitant medications (limited to AAD and anticoagulants) will be documented. Routine medications, including AAD may be continued. Symptomatic AF or flutter should be treated with AAD or cardioversion as needed but will not be recorded for endpoint assessment.
- 3. Three-month (90D) follow-up (+/- 30 days).** Evaluation will include an EKG, and assessment for complications, targeted physical exam and a review of adverse events and concomitant medications (limited to AAD and anticoagulants) will be documented. If the patient is in AF or flutter, a cardioversion will be performed electively within 2 weeks so that all patients are in sinus rhythm after the 3 month blanking period. AAD therapy will be discontinued in all patients at this time if they are clinically stable and in sinus rhythm.
- 4. Six-month (180D) follow-up up (+/- 60 days).** Follow up evaluation will include an EKG, and physical exam. Additionally, patients will fill out the AFEQT¹¹³ QOL questionnaire and will undergo a 3-4 week continuous EKG monitor (4 weeks if tolerated by patient) (see *Core laboratories*, below). Subjects who have a miniaturized, implantable rhythm recording device (such as Medtronic LinQ and others) or an implanted pacemaker/defibrillator may have the continuous rhythm data obtained from that device, and may forego the portable recorder. The purpose of this EKG monitor (4 weeks if tolerated by patient) is to screen for recurrent AF that may prompt an early repeat procedure. Patients that have clinical or EKG recurrences will undergo a PVAI procedure (see below and Figure 8).
- 5. Nine-month follow-up up (+/- 30 days).** Follow up evaluation will include an EKG and physical exam. Patients that have clinical or EKG recurrences will undergo a repeat PVAI procedure. The timing of a repeat procedure will be encouraged to be within 6 months of randomization.
- 6. Twelve-month follow-up up (+/- 60 days).** Follow up evaluation will include an EKG, and physical exam. Additionally, patients will fill out the AFEQT¹¹³ QOL questionnaire

and undergo a continuous EKG monitor (4 weeks if tolerated by patient) to determine the primary efficacy endpoint.

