Subjects who have a miniaturized, implantable rhythm recording device (such as Medtronic LinQ and others) or an implantable pacemaker/defibrillator may have the continuous rhythm data obtained from that device, and may forego the portable recorder.

Patients will fill out the AFEQT¹¹³ QOL questionnaire. Additionally, echocardiographic assessment of LA function (LA ejection fraction, strain^{114ab}) will be performed by a central reader at Houston Methodist Hospital.

—

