- e. Documentation of RF time, time to perimitral block (if not already achieved), fluoroscopy time, LA instrumentation time, and procedure time.
- f. Baseline and Final LA voltage map (using any commercially available electroanatomical mapping systems). Measurement of baseline and Final LA scar surface area.

4. Effectiveness (Treatment) Failures

Effectiveness failures towards the primary endpoint will include the following (see Figure 8):

- a. Clinical recurrence of AF or AT after 3-months.
- b. Documented AF or AT of 30 seconds or more on EKG monitor at obtained at 6 and 12 months.
- c. Requirement of a repeat ablation procedure for recurrent AT-AF.
- d. Death.

VENUS and MARS patients who have a recurrence after 3 months post randomization will have a repeat procedure (PVAI). Patients will be deemed to be effectiveness failure for the primary efficacy endpoint of the trial after repeat procedures. Still, subjects will:

- a. Remain in the study for the purpose of all secondary endpoints: these include quality of life, AF burden on event monitoring, success after multiple procedures.
- b. Undergo all clinically necessary procedures and treatments, including prescription of antiarrhythmic therapy and additional procedures needed to control atrial fibrillation or flutter. A crossover VOM procedure will be offered to those randomized to PVAI after 2 in-study procedures.
- c. Data on such additional procedures or treatment will be collected in the Electronic Data Capture system (EDC).
- d. An additional secondary endpoint will be created: total number of procedures performed and requirement of antiarrhythmic drugs.

5. VENUS: Cross-over of patients initially randomized to PVAI only.

If a VENUS patient is originally randomized to conventional PVAI and experiences a treatment failure after a repeat procedure he or she may undergo an additional conventional PVAI ablation procedure during the study. Crossover to VOM ethanol will only be allowed after 2 procedures are performed in the setting of study participation. This is allowed because certain recurrent flutters are particularly suited to respond to VOM ethanol. The primary and secondary endpoints will be computed following their original randomization group.

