- (j) For subjects who undergo repeat on-study procedures, mapping will be done a second time
- (k) Echocardiogram for LA Strain will be performed at study end at 12 months, and read centrally by core lab.
- (l) Imaging prior to enrollment is required to rule out the presence of LA appendage thrombus. Ruling out LAA thrombus can be performed by the following: TEE within 48 hours of the procedure; at least one month of oral anticoagulation prior to the procedure; or documented prior procedures of LAA occlusion or ligation.
- (m) Imaging prior to enrollment is required to rule out structural heart disease. For ruling out structural heart disease, either a cardiac MRI or CT or transthoracic echocardiogram within 1 year prior to participation in the study is sufficient.
- (n) Options for continuous EKG monitoring include: event monitoring include: external event monitor, implanted miniaturized rhythm monitor, or implanted pacemaker.

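### An implanted device may replace the continuous ECG for the primary endpoint, but nothing requires that it can register AF/AT of 30 seconds

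*Combined protocol and SAP*

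**What the plan says.** **Threshold.** Section 5.2 sets the primary efficacy endpoint at less than 30 seconds of AT/AF on monitoring, together with freedom from clinical recurrence. Section 5.7 item 4b lists as a treatment failure "Documented AF or AT of 30 seconds or more on EKG monitor at obtained at 6 and 12 months"; section 5.8 item 4 repeats this for MARS. The other routes to failure are clinical recurrence after month 3, repeat ablation and death.

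**Substitution.** At the 6-month visit (5.6 item 4), subjects with an implantable recorder or "an implanted pacemaker/defibrillator may have the continuous rhythm data obtained from that device, and may forego the portable recorder". The 12-month visit (5.6 item 6) gives the same permission: "an implantable pacemaker/defibrillator may have the continuous rhythm data obtained from that device, and may forego the portable recorder". Footnote (n) to the schedule in 7.1 lists the options as "external event monitor, implanted miniaturized rhythm monitor, or implanted pacemaker" and does not mention defibrillators. Section 7.7 does not name them either.

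**Role in the endpoint.** For patients who already have a pacemaker, 7.7 says "AF data will be quantified for the primary and secondary endpoints using these devices as opposed to 3-4 week electrocardiographic monitoring". It has a parallel sentence for implanted recorders.

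**Capability.** For pacemakers, 7.7 states: "These devices yield interrogation reports that provide sufficient data on atrial fibrillation or flutter burden, episode duration per day and other quantified data". For recorders it names one model "or other equivalent implanted permanent monitoring devices", without defining equivalence. No section sets a requirement for atrial sensing, a shortest detectable episode, device programming or stored tracings.

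**How many.** Not stated. Section 7.7 says only "Certain patients may already have an implanted pacemaker previously inserted prior to study enrollment".

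**The concern.** The external monitor suits a 30-second threshold because 7.7 has the vendor store every heart beat. A device summary is a different measurement. Burden and daily episode duration can be reported without every episode of 30 seconds being captured. If a device logs only episodes longer than some setting D, those between 30 seconds and D leave no trace.

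Two safeguards might be expected to catch this, and neither does. The missing-data rule in section 6.0 depends only on monitored time (at least one week), so a device that ran for four weeks satisfies it whatever its detection limit. Blinded adjudication (7.6) covers implanted devices, but it sets no detection standard and cannot review an episode that was never recorded.

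At stake is a primary endpoint whose detection limit may vary with the hardware a patient has. Recurrences missed at random add more apparent successes to the arm with more failures. That narrows the treatment difference and overstates success in both arms.

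**Working it through.** **1. Inputs from the plan (section 6.0 B, Table 6).** True success 0.56 (VOM-PV) and 0.38 (PVAI); looks at 60/52, 120/104 and 180/156 patients; bounds 3.953, 2.543 and 2.011; unpooled Z-test; two-sided alpha 0.05.

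**2. The plan's own figure.** Simulating this design (400,000 runs) gives power 0.910, against 0.909 stated. The fixed-sample formula gives 0.913. Simulated type I error at 0.38 in both arms is 0.0494, against 0.049 stated. The stated power is reproduced.

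**3. Assumed inputs, which the documents do not give.**
- f: share of patients assessed by an implanted device, equal in both arms.
- m: share of those patients' failures that the device does not register and that are not found clinically, on a visit EKG or through repeat ablation.

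**4. Formula.** A true failure is counted as a success with probability f × m. For true success p:

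observed success = p + f × m × (1 − p)

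The observed difference is therefore 0.18 × (1 − f × m).

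Example with f = 10%, m = 30%, so f × m = 0.03:
- VOM-PV: 0.56 + 0.03 × 0.44 = 0.573
- PVAI: 0.38 + 0.03 × 0.62 = 0.399
- Difference: 0.18 × 0.97 = 0.175

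**5. Results over a range (group-sequential simulation; differences from unrounded rates).**

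| f | m | VOM-PV | PVAI | Difference | Power |
|---|---|---|---|---|---|
| none | none | 56.0% | 38.0% | 0.180 | 0.910 |
| 5% | 10% | 56.2% | 38.3% | 0.179 | 0.907 |
| 10% | 30% | 57.3% | 39.9% | 0.175 | 0.891 |
| 20% | 30% | 58.6% | 41.7% | 0.169 | 0.871 |
| 20% | 50% | 60.4% | 44.2% | 0.162 | 0.839 |
| 20% | 100% | 64.8% | 50.4% | 0.144 | 0.754 |

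The last row is a limit, not an expectation: every failure among device patients would have to escape both the device and clinical follow-up.

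**6. MARS.** The same provisions apply and the planned difference shrinks by the same factor. At f = 10%, m = 30% it is 0.34 × 0.97 = 0.330.

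**7. Unequal device use, with no true effect (38% in both arms).** With m = 50%, use of 10% versus 5% gives 0.38 + 0.05 × 0.62 = 0.411 versus 0.38 + 0.025 × 0.62 = 0.396, and a two-sided rejection rate of 0.060. Use of 20% versus 10% gives 0.442 versus 0.411, and 0.089.

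**The case against.** **The permission is not as open as it may look.** A reader might infer that any implanted device qualifies, including one with no atrial sensing. The documents do not support that. Section 5.6 speaks of continuous rhythm data obtained from the device, and 7.7 describes devices that report AF or flutter burden. A device that cannot do so lies outside what 7.7 describes. This stands. What remains open is the detection limit of devices that do report burden.

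**Device silence is not automatically success.** A reader might infer that every unregistered recurrence is scored as a success. It is not. Clinical recurrence, repeat ablation and death still count as failures, and an EKG is done at each scheduled clinic visit. A device with no usable atrial data could also be handled as missing (section 6.0, Missing data) or unclassifiable and excluded (section 6.0 A); the plan does not say which. This too stands. It confines the problem mainly to brief or asymptomatic episodes, which are what continuous monitoring is there to find.

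**A false positive is not shown.** Step 7 shows that unequal device use could raise type I error. Patients may choose a recorder and operators are unblinded, so imbalance is possible, but the documents give no evidence of it. With equal use the bias runs toward no difference.

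**Device patients may be observed longer.** An external recording counts with as little as one week of wear, whereas 7.7 describes recorders as continuous for up to three years. This could offset some missed episodes. The model isolates detection and does not establish the net bias for a device patient.

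**No passage says that a permitted device misses 30-second episodes.** True. The gap is that none requires that it must not.

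**Conclusion.** The gap is certain from the text; its size is not. The plan lets device data decide a 30-second endpoint without a 30-second capability requirement, and its lists of permitted devices disagree on defibrillators. Some brief or asymptomatic recurrences can therefore be scored as successes, and the detection limit may differ between patients.

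The effect is probably modest. Under equal use in both arms, power is about 89% instead of 91% at 10% device use with 30% of failures missed, and the change is negligible at 5% and 10%. Larger losses need heavier device use or much higher miss rates than the documents give reason to expect. All these figures rest on assumed f and m. The change is still worth making before analysis, because a recurrence that was never recorded cannot be recovered later and prevention is cheap.

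**What to change.** - In 5.6 items 4 and 6, 7.1 footnote (n) and 7.7, allow substitution only when the device, as programmed, can document AF and AT episodes of 30 seconds over the 6- and 12-month monitoring windows, in a form the blinded ECG laboratory can adjudicate. Other device patients wear the external monitor already supplied in the trial.
- Make the device list consistent across those sections, stating whether defibrillators are included.
- Record device type and detection setting for every patient assessed by an implanted device.
- Add a sensitivity analysis of the primary endpoint that excludes patients assessed by a device not meeting the rule.

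**Cost.** One capability sentence carried through these sections, one or two data fields and one extra analysis. Some device patients, in a number the documents do not allow us to estimate, would also have to wear the external monitor.

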7.8 SAFETY CONSIDERATIONS

Ethanol infusion for the treatment of hypertrophic cardiomyopathy has been used for more than a decade.¹²⁴ Complications derive from collateral damage (i.e. AV block) or spillage of ethanol in unintended arterial branches.¹²⁴ VOM infusion is retrograde, and spilled ethanol drains via the CS into the right atrium to be diluted to non-damaging concentrations. Ethanol passage into the systemic circulation via the LA, albeit seemingly dangerous, is necessary for its ablative effects in the atrial myocardium. In order to achieve rapid dilution and avoid systemic effects, a slow infusion rate is critical. Mixed blood ethanol have been undetectable. VOM venograms performed after VOM ethanol infusion can show varying degrees of myocardial staining, but macroscopic extravasation into the epicardial space has not occurred. Adverse events of the VOM procedure included one CS dissection, which had no clinical consequences. Two patients developed sub-acute pericardial effusion 4 and 6 weeks after the procedure, respectively. The role of VOM ethanol is unclear, since this complication is also well described in conventional ablation.⁵⁶ No systemic effects were

detected at the doses tested (total 4 ml). This is an FDA Investigational New Drug (IND # 105083) project, which will continue.

Added procedure and fluoroscopy times in our previous experience average 45 and 8 minutes, respectively. Reported fluoroscopy times of conventional ablation can be up to 100-120 minutes,^{125, 126} so 8 minutes do not represent a major fluoroscopy time increase. Given that VOM ethanol may lead to ablation of otherwise targeted tissue (including LIPV isolation),¹ and facilitate perimetal block,³ it may reduce the need of RF ablation in these areas. Thus VOM ethanol may potentially save procedure and fluoroscopy times downstream.

7.8.1 Adverse Event Reporting

The adverse event reporting period for this trial begins at the time the subjects sign the informed consent form, and will continue through the final month follow-up visit or withdrawal from the study. Reportable events will be reported per institution specific IRB policy.

Only AE's related to the catheter ablation procedure, ethanol ablation, and disease process will be captured.

Anticipated (Expected) Adverse Events (AE's)

Patients may experience certain clinical events that are attributable to the ablation procedure or the disease process of the patient. ***The following list of AE's are expected based on previous clinical and research experience.***

- Atrial Arrhythmias
- Chest pain or Angina
- Standard of care cardioversions for arrhythmias
- Headache
- Minor bleeding
- Hypertension or hypotension
- Vasovagal reactions
- self-limiting pericarditis attributable to the ablation procedure defined as pleuritic chest discomfort with or without pericardial rub
- pacemaker implantation for nodal dysfunction rhythms (sick sinus syndrome, sinus bradycardia, sinus arrest or AV blocks) that resulted in symptomatic bradycardia (unrelated to the ablation procedure or related to pre-existing disease state)
- Incision site pain/soreness
- Incision site infection
- Inadvertent AV block: Second or third degree heart block
- Palpitations
- Pulmonary edema
- ECG changes that did not require additional hospitalization
- Pericarditis
- Anxiety
- Hematoma

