5.2 STUDY ENDPOINTS

Primary endpoints:

1. Primary Efficacy Endpoint Freedom from AT/AF clinical recurrence on follow-up visits AND less than 30 seconds of AT/AF on a 1 month continuous electrocardiographic monitor at 6 and 12 months.
2. Primary Safety Endpoint - Acute procedural complications and total mortality.

Secondary Endpoints

1. Freedom from AF/AT after >1 procedure.
2. Freedom from AF/AT on antiarrhythmic drugs.
3. AF burden (% time) on continuous monitoring at 6 and 12 months.
4. Procedural parameters: total procedure, fluoroscopy, total RF ablation time (first procedure), and total extent of ablated LA tissue.
5. Clinical/partial success: less than 25% AF burden on a continuous event monitor at 6 and 12 months from ablation procedure.
6. Sub-acute procedural complications (within 30 days).
7. Recurrence as persistent or paroxysmal AF, or flutter after 1 or 2 procedures.

8. LA function on Doppler echocardiography (LA strain^{114ab}) at 12 months.
9. Incidence and mechanisms of atrial flutters.
10. Cardiovascular hospitalizations and
11. QOL as determined by AFEQT questionnaire.

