1. Freedom from symptomatic AF or flutter AND reduction of AF/flutter to less than 30 seconds in a continuous 4 week monitor at 6 and 12 months	
 12 month continuous ECG page- MARS 12 month continuous ECG page- Venus 	
 6-12 month AF/AT Burden less than 30 seconds on continuous ECG monitoring
2. Safety: Acute procedural complications	
 AE pages Day 7 Telephone FU 	
 Acute AE's related to Day 0 procedure Day 7 reported complications
Secondary Endpoints:		
1. Single vs. 2-procedure success.	
 Status change page 	
 Single: reached primary endpoint #1 after first procedure with no repeats Two procedure: reached primary endpoint #1 after second procedure with no 3rd procedure
2. AF burden (% time) on continuous monitoring at 12 months.	
 6-12 month continuous ECG page- MARS 12 month continuous ECG page- Venus 	
 6- 12 month AF/AT Burden (%) on continuous ECG monitoring
3. Procedural parameters: total procedure, fluoroscopy, total RF ablation time (first procedure), and total extent of ablated LA tissue.	
 PVAI Page VOM page 	
 Total procedure time, PVAI only Total procedure time, VOM procedure Total fluoro time Scar measurements pre and post PVAI and VOM
4. Clinical success: freedom from symptomatic AF/flutter but AF/flutter > 1 min/day < than 1% at 12 months.	
 12 month continuous ECG page- MARS 12 month continuous ECG page- Venus 	
 12 month AF/AT Burden less than 25% continuous event monitor at 6 and 12 months from ablation procedure
5 Sub-acute procedural complications (within 30 days).	
 Symptoms page AE page 	Day 30 reported, procedure related complications via symptoms and/or AEs
6 Recurrence as persistent or paroxysmal AF, or flutter after 1 or 2 procedures.	
 12 lead Ecg page Evaluation for repeat procedure page AE page 	
 Type of recurrence (rhythm) Characterization of recurrence e.g. persistent or paroxysmal for a fib; typical or atypical for a flutter.
7. LA function on Doppler echocardiography (LA strain114ab) at 12 months.	Central echocardiogram page	LA Strain

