Missing data. The critical piece of data required for endpoint analysis is the electrocardiographic event monitor. Failure to comply with wearing the monitor will lead to missing data. We request patients to wear monitors for 1–month. However, only a minimum of 1-week of monitored time is required for Endpoint assessment. Patients with less than 1 –week of monitoring will be considered as missing data. Patients who die before then study end will be considered not to have a response to treatment. For patients with missing primary outcomes, we will perform multiple imputation (MI) based on Monte Carlo Markov chain (MCMC) methods (Refs 1-3). MI will only be used for dealing with missing data as a secondary analysis tool of the primary endpoint. In Stata, MI is available for many procedures, especially the regression modules (linear, logistic, Poisson, Cox PH). MI can be performed to iteratively impute central estimates of missing outcome measures based on subjects' covariate patterns. The most straightforward example can be envisioned in this study, where logistic regression with MI is employed to train a model based on primary outcome (0-failure,1-success) as the dependent variable and age, gender, baseline AF duration, and baseline LA volume as independent predictors to impute $P(y=1|x)$ for subjects with missing primary outcome.

Sensitivity analysis. Following methods introduced in Proschan et al. (Ref 4), we simulated success rates for patients with missing 12-month outcomes in VOM and PVAI arms for VENUS and MARS at 33%, 66%, and 100% information time (looks 1-3). $B=100,000$ iterations were used with proportions of $P_m=0, 0.05, 0.10, 0.15$, and 0.2 representing the amount of missing data in both VOM and PVAI arms. At look k , let the success rate in the VOM arm be p_{1k} and the success rate in the PVAI arm be p_{2k} , n_{1k} and n_{2k} the number of patients accrued in the VOM and PVAI arms, $n_{1k}^m = n_{1k}P_m$ and $n_{2k}^m = n_{2k}P_m$ the number of patients in VOM and PVAI arms with missing outcome data, and $n_{1k}^0 = n_{1k} - n_{1k}^m$ and $n_{2k}^0 = n_{2k} - n_{2k}^m$ the number of patients in VOM and PVAI arms without missing outcomes. Next, for VOM patients with missing

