	0.15	1.000	1.000	0.977	0.903	0.619
	0.2	0.984	0.939	0.734	0.516	0.369
0.86	0	1.000	1.000	1.000	1.000	1.000
	0.05	1.000	1.000	1.000	1.000	1.000
	0.1	1.000	1.000	1.000	1.000	1.000
	0.15	1.000	1.000	1.000	0.981	0.913
	0.2	1.000	0.986	0.944	0.852	0.619

D) Stopping rules. The trials will be stopped if one of the following occurs:

- Futility/efficacy boundaries reached. As illustrated in Figures S1 and S2, if the upper or lower boundary is reached at the 1/3 or 2/3 data assessment for beneficial efficacy or futility respectively, the trial will be evaluated for early termination.
- Safety. Events will be reported to FDA, NHLBI, and DSMB according to FDA/OHRP requirements and NHLBI adverse event and unanticipated problem reporting policy. Expedited reporting will occur within 7 days of initial receipt of information for fatal or life-threatening unexpected serious reactions and within 15 calendar days for non-fatal, non-life threatening unexpected events. The DSMB will otherwise evaluate overall safety events on a bi-annual basis. An excess of **procedural** adverse events attributable to study procedure will be evaluated for early termination. Procedural adverse events include those that occur within 24 hours of the procedure or those that may be delayed but procedure-related (atrio-esophageal fistula or delayed pericardial effusion). The following are expected to be rare. One event may occur by chance in either treatment groups. Two of the same events in either arm will trigger consideration for study termination after detailed case review:
 - Mortality.
 - Stroke-Transient ischemic attack or systemic embolus.
 - Pericardial effusion requiring drainage

- Raghunathan, T. E., J. M. Lepkowski, J. Van Hoewyk, and P. Solenberger. 2001. A multivariate technique for multiply imputing missing values using a sequence of regression models. *Survey Methodology* 27: 85–95.
- Rubin, D. B. 1987. *Multiple Imputation for Nonresponse in Surveys*. New York: Wiley.
- van Buuren, S. 2007. Multiple imputation of discrete and continuous data by fully conditional specification. *Statistical Methods in Medical Research* 16: 219–242.

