7.2 PATIENT RECRUITMENT, PROCEDURES AND FOLLOW-UP

Patients will be recruited from Cardiac Electrophysiology consultation services at all sites. Qualified, trained investigators will perform the procedures at the centers. These investigators will be unblinded. Patients will be followed up by qualified and trained at each study center.

The clinicians will follow the patients and evaluate adverse events and clinical primary endpoints.

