7.6 BLINDING

Patients and personnel involved in data analysis, will be blinded to the treatment provided. Upon enrollment, the operators will be informed of the randomization outcome. After the procedure is performed, data will be collected and analyzed with treatment groups as the only identifier. The DSMB will receive the data identification for their assessment.

The primary endpoint of freedom from AF as determined by electrocardiographic monitoring by either external monitors or implanted devices will be adjudicated *in an independent and blinded manner* by the external EKG monitoring laboratory, respectively.

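### Adverse events are recorded only if judged related, with no stated assessor or blinded safety review, and read literally the rule conflicts with the total-mortality endpoint

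*Combined protocol and SAP*

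**What the plan says.** **Capture rule.** Section 7.8.1 limits adverse event recording: "Only AE's related to the catheter ablation procedure, ethanol ablation, and disease process will be captured". Reporting runs from consent to the final visit or withdrawal. Section 7.8.2 defines a serious adverse event as an adverse event that meets further criteria, so serious events are a subset of what 7.8.1 admits.

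**Endpoint.** Section 5.2 gives "Primary Safety Endpoint - Acute procedural complications and total mortality". In Section 6.0, the table linking endpoints to data pages has a row reading "Safety: Acute procedural complications". It draws on the adverse event pages and the day 7 call, and its first data field is "Acute AE's related to Day 0 procedure". The row does not mention mortality.

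**Deaths.** Section 6.0 A says mortality will be recorded for safety. Sections 5.7 and 5.8 (item 4) list death as an effectiveness failure. The missing-data text in Section 6.0 says "Patients who die before then study end will be considered not to have a response to treatment". None of these is limited by cause.

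**Who knows the arm.** Section 7.6 states: "Upon enrollment, the operators will be informed of the randomization outcome". Section 7.2 says of those performing the procedures: "These investigators will be unblinded". Section 7.2 also gives adverse event evaluation to the follow-up clinicians, and Section 9.4 intends the clinicians who follow the primary endpoints to be blinded. Independent blinded adjudication is described in Section 7.6 only for AF found on rhythm monitoring.

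**The concern.** Randomisation protects a comparison of all events. It does not protect a comparison of events that someone has first chosen to attribute. Here attribution decides whether an event is recorded at all, when it could have been a field recorded alongside it. If events after the added ethanol step are called unrelated more often, or less often, than events after ablation alone, the safety comparison shifts and the adverse event data hold nothing with which to test for it.

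The consequences of attribution also differ by arm. Under Section 7.8.2, an unexpected serious event judged at least possibly related to the VOM procedure puts the study on hold, and no matching rule is given for the control procedure. Attribution can be hard: Section 7.8 reports two late pericardial effusions in earlier experience and says the part played by ethanol is unclear.

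Deaths raise a separate question, because the endpoints need every death while the capture rule, taken at its word, would leave out a death judged unrelated.

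**Working it through.** The plan gives no rate, margin, test or power for the safety endpoint, so there is no safety figure to reproduce. The check is a reading of the rules, followed by an illustration on assumed rates.

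**1. Follow an event through the rules.**
- Related to ablation, ethanol or AF (7.8.1): recorded. Moving an event between these three categories does not lose it.
- Called unrelated to all three: not recorded as an adverse event. Because serious events are a subset (7.8.2), this applies to them too.
- During the procedure: the data list at the end of Section 4.2 collects procedural complications of any kind in all patients. This limits the loss, but someone must still call the event procedural.
- In the first day: the stopping rules in Section 6.0 D say "Procedural adverse events include those that occur within 24 hours of the procedure or those that may be delayed but procedure-related". The first half of that definition needs no attribution. It appears only under the stopping rules, and the endpoint table does not use it.
- Later: the day 7 call and the 30-day field are both worded in terms of procedure-related or disease-related complications.

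**2. Who applies the filter.** No section assigns the relatedness judgement. Operators are unblinded (7.2, 7.6). Follow-up clinicians are meant to be blinded (7.2 with 9.4). The day 7 call is made by a coordinator (5.6) whose blinding is not stated.

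**3. Deaths.** Sections 5.2, 5.7, 5.8 and 6.0 require deaths from any cause. Section 7.8.1 read literally excludes an unrelated one, the table's safety row has no place for it, and reporting stops at withdrawal. If a death did go unrecorded, the patient could look unclassifiable and be dropped under Section 6.0 A when a failure should be counted. The effect on efficacy is small: one such patient in the VENUS VOM-PV arm moves 0.56 to (0.56 × 180)/179 = 100.8/179 = 0.563, and one in the PVAI arm moves 0.38 to (0.38 × 156)/155 = 59.28/155 = 0.382.

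**4. Illustration (VENUS, 180 VOM-PV and 156 PVAI; rates and capture fractions are assumed).** Recorded rate = true rate × fraction captured; expected events = arm size × recorded rate.

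| True rate, VOM-PV / PVAI | Captured | Recorded rate | Expected events | Recorded difference (points) |
|---|---|---|---|---|
| 5% / 5% | 100% / 100% | 5.0% / 5.0% | 9.0 / 7.8 | 0 |
| 5% / 5% | 90% / 90% | 4.5% / 4.5% | 8.1 / 7.0 | 0 |
| 5% / 5% | 80% / 100% | 4.0% / 5.0% | 7.2 / 7.8 | -1.0 |
| 5% / 5% | 100% / 80% | 5.0% / 4.0% | 9.0 / 6.2 | +1.0 |
| 10% / 5% | 100% / 100% | 10.0% / 5.0% | 18.0 / 7.8 | +5.0 |
| 10% / 5% | 80% / 100% | 8.0% / 5.0% | 14.4 / 7.8 | +3.0 |
| 10% / 5% | 60% / 100% | 6.0% / 5.0% | 10.8 / 7.8 | +1.0 |
| 10% / 5% | 100% / 80% | 10.0% / 4.0% | 18.0 / 6.2 | +6.0 |

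Power of a two-sided 5% comparison is Φ[(d − 1.96·se0)/se1], with se0 from the pooled rate and se1 from the separate rates. At full capture of 10% v 5%, d = 0.05, se0 = 0.0291 and se1 = 0.0284, so (0.05 − 0.0571)/0.0284 = −0.25 and power is 0.40. With VOM-PV capture of 80%, 70% and 60% it is 0.19, 0.11 and 0.06.

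**The case against.** The other side has several good points.

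- **The filter is broad.** It admits disease-process events, and the expected-event list in 7.8.1 even includes pacemaker implantation unrelated to the ablation. An event is lost only if it is called unrelated to all three categories. This stands and narrows the concern.
- **The endpoint is procedural by definition.** Limiting acute procedural complications to procedural events is part of what the endpoint means, and Sections 4.2 and 6.0 D soften the filter in the acute window. This stands for the procedure itself and the first 24 hours. It does not cover delayed events or serious events called unrelated, and the 24-hour wording is not tied to the endpoint.
- **Mortality is covered.** A reader might infer that all-cause deaths will not be collected. The documents do not support that: Sections 5.2, 5.7, 5.8 and 6.0 all count deaths without regard to cause. What remains is a conflict with 7.8.1 and a gap in the table.
- **Blinding.** A reader might infer that all adverse event assessment is done by people who know the arm. That is not shown, since the follow-up clinicians are meant to be blinded. Operators do know the arm, and the assessor of relatedness is unnamed.
- **Recoverability.** Source records are kept (9.2), monitors review adverse events (9.3) and the DSMB sees unblinded reports (7.8.3). Some missed events might therefore be found at sites, but none of these provisions puts an unrelated event into the data to be compared by arm.

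**Conclusion.** The point holds in a limited form. The capture rule makes attribution a condition of being recorded, the primary safety field repeats that condition, no assessor is named, and no blinded adjudication of safety events is described. Events called unrelated to all three categories, including serious ones, cannot be compared between arms from the adverse event data. The mortality element is an inconsistency between sections; it does not show that deaths will be missed.

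The documents do not allow the size or direction of any bias to be determined. It would be tempting to conclude that the rule hides harm from ethanol. The text does not support this: loss could fall on either arm, and equal loss creates no false difference, although it would shrink a real one in proportion. The illustration shows only sensitivity. At an assumed 5% in both arms, losing a fifth of events in one arm gives a 1-point gap. At an assumed 10% v 5%, capturing 60% to 80% of VOM-PV events and all PVAI events shrinks a 5-point excess to between 1 and 3 points. This is worth changing because the remedy is cheap.

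**What to change.** 1. In Section 7.8.1, capture all deaths and all serious adverse events from consent to study end regardless of attribution. Record relatedness as a field and state who completes it.
2. Add all-cause death to the safety row of the endpoint table in Section 6.0, so that it matches Section 5.2.
3. Apply the attribution-free 24-hour definition in Section 6.0 D to the primary safety endpoint. For this to work, every adverse event in that window must be entered whatever its attribution.
4. Compare the arms on all captured deaths and serious events, with related events as supportive.

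The cost is a few sentences, a relatedness field and a death item on the case report form, and some extra entries at sites, mainly serious events and those in the first 24 hours. Capture of every non-serious event out to 30 days is not needed to resolve the point. No treatment changes.
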